10.1 DEFINITION OF ADVERSE EVENTS

Adverse event (AE) means any untoward medical occurrence in a patient or subject administered a medicinal product; the untoward medical occurrence does not necessarily have a causal relationship with this treatment. An AE can therefore be any unfavorable and unintended sign, symptom, or disease temporally associated with the use of an investigational medicinal product (IMP) or other protocol-imposed intervention, regardless of attribution.

An adverse event includes the following:

- Signs or symptoms that were not present or observed in the patient prior to the AE reporting period and that emerge during the protocol-specified AE reporting period (i.e. TEAEs)
- Complications that occur as a result of protocol-mandated interventions (e.g. invasive procedures such as biopsy)
- If applicable, AEs that occur prior to assignment of study treatment associated with medication washout, no treatment run-in, or other protocol-mandated intervention
- Pre-existing medical conditions (other than the condition being studied) judged by the investigator to have worsened in severity or frequency or changed in character during the protocol-specified AE reporting period
- Abnormal laboratory values or diagnostic test results constitute AEs only if they induce clinical signs or symptoms, require treatment or further diagnostic tests, or lead to discontinuation or delay in treatment, or if it represents a clinically significant change from baseline as determined by the investigator
- Progressive disease will not be considered an adverse event.

Adverse events and laboratory results will be coded using the Medical Dictionary for Regulatory Activities (MedDRA) and the severity of adverse events will be graded using the scales found in the revised NCI Common Terminology Criteria for Adverse Events (CTCAE) version 5.0 will be utilized for AE reporting. http://ctep.cancer.gov/protocolDevelopment/electronic_applications/ctc.htm. Hematologic toxicity will be graded by CLL criteria [37] and can be found in Appendix 2. For adverse events not covered by the NCI-CTCAE Version 5.0 grading system, the following definitions will be used:

- **Grade 1:** Mild; asymptomatic or mild symptoms; clinical or diagnostic observations only; intervention not indicated.
- **Grade 2:** Moderate; minimal, local or non-invasive intervention indicated.
- **Grade 3:** Severe or medically significant but not immediately life-threatening; hospitalization or prolongation of hospitalization indicated.
- **Grade 4:** Life-threatening consequences; urgent intervention indicated.
- **Grade 5:** Death related to AE.

10.2 SERIOUS ADVERSE EVENTS (SAE)

An AE should be classified as an SAE if the following criteria are met:

- It results in death (i.e. the AE actually causes or leads to death)
- It is life threatening (i.e. the AE, in the view of the investigator, places the patient at immediate risk of death. It does not include an AE that, had it occurred in a more severe form, might have caused death)
- It requires or prolongs inpatient hospitalization, but not to include routine hospitalizations for neutropenic fevers that do not result in sepsis syndrome and/or ICU transfer
- It results in persistent or significant disability/incapacity (i.e. the AE results in substantial

- disruption of the patient's ability to conduct normal life functions)
- It results in a congenital anomaly/birth defect in a neonate/infant born to a mother exposed to the investigational product
- It is considered a significant medical event by the investigator (e.g. may jeopardize the patient or may require medical/surgical intervention to prevent one of the outcomes listed above).

Clarification should be made between an SAE and an AE that is considered severe in intensity (Grade 3 or 4), because the terms serious and severe are NOT synonymous. The general term *severe* is often used to describe the intensity (severity) of a specific event; the event itself, however, may be of relatively minor medical significance (such as a Grade 3 headache). This is NOT the same as *serious*, which is usually associated with events that pose a threat to a patient's life or ability to function. A severe AE (Grade 3 or 4) does not necessarily need to be considered serious. For example, a white blood cell count of 1000/mm³ to less than 2000 is considered Grade 3 (severe) but may not be considered serious. Seriousness (not intensity) serves as a guide for defining regulatory reporting obligations.

10.3 EXPECTEDNESS OF ADVERSE EVENTS

Expected adverse events are those that have been previously identified as resulting from administration of the agents. For the purposes of this study, an adverse event is considered expected when it appears in the investigational brochure, the package insert or is included in the informed consent form as a potential risk. An adverse event is considered unexpected when it varies in nature, intensity or frequency from information provided in the current adverse event list, the investigational brochure, the package insert, in published medical literature, in the protocol, or is not included in the informed consent form as a potential risk.

10.4 ATTRIBUTION OF ADVERSE EVENTS

The investigator must attempt to determine if there exists reasonable possibility that an AE or SAE is related to the use of the investigational treatment. Attribution of adverse events should be described as treatment related or not related. To ensure consistency of AE and SAE causality assessments, investigators should apply the following general guidelines when determining if an AE or SAE is treatment-related:

- **Treatment-Related:** There is a reasonable causal relationship between the investigational treatment and the adverse event. There is a plausible temporal relationship between the onset of the AE and administration of the investigational treatment, and the AE cannot be readily explained by the patient's clinical state, intercurrent illness, or concomitant therapies; and/or the AE follows a known pattern of response to the investigational treatment; and/or the AE abates or resolves upon discontinuation of the investigational treatment or dose reduction and, if applicable, reappears upon re-challenge.
- **Not Treatment-Related:** There is no reasonable causal relationship between the investigational treatment administered and the adverse event. Evidence exists that the AE has an etiology other than the investigational treatment (e.g. pre-existing medical condition, underlying disease, intercurrent illness, or concomitant medication); and/or the AE has no plausible temporal relationship to administration of the investigational treatment.

10.5 RECORDING/REPORTING ADVERSE EVENTS

AEs experienced by participants will be collected and reported from initiation of investigational treatment (to also include events preceding initiation of study treatment if an AE is at least possibly related to withholding medication prohibited by protocol, or a study procedure such as a biopsy), throughout the study, and within 30 days after the last dose of study medication. All SAEs regardless of grade, severe AEs (i.e. Grade ≥ 3), and events of death will be recorded, regardless of event attribution. Baseline disease-related signs and symptoms which are initially recorded as medical history, will subsequently be recorded as adverse events during the trial if they worsen in severity or increase in frequency. Participants should be instructed to report any serious post-study event(s) that might reasonably be related to participation in this study. The investigator should notify the IRB and any other applicable regulatory agency of any unanticipated death or serious adverse event occurring after a participant has discontinued or terminated study participation that may reasonably be related to the study. Follow-up for SAEs should continue until resolution, stabilization, the subject has withdrawn consent or has been lost to follow-up.

- Further AE reporting procedures are as follows:
 - Serious adverse events must be reported to the Study Chair from the first dose of protocol-indicated treatment up to and including 30 days after administration of the last dose of investigational agent.
 - All AEs, regardless of grade, and events of death of any patient during the course of the trial will be reported in the case report form, and the investigator will give his or her opinion as to the relationship of the adverse event to trial drug treatment.
 - Asymptomatic abnormal laboratory values of Grade 1 or Grade 2 that do not trigger dose interruption or modification of protocol-indicated treatment will be deemed not clinically significant and are not required to be individually noted or recorded within the study data.
 - Laboratory and vital sign abnormalities are to be recorded as AEs only if they are medically relevant as judged by the investigator (e.g. symptomatic, requiring corrective treatment, leading to discontinuation of protocol-indicated treatment, and/or fulfilling a seriousness criterion).
 - Since this is an investigator-initiated study, the principal investigator, also referred to as the study chair, is responsible for reporting SAEs to any regulatory agency and to the study chair's data safety monitoring committee (DSMC) and IRB.
 - Fatal and life-threatening SAEs must be reported within 24 hours of the study chair's observation or awareness of the event to the DSMC chairperson or designee
 - All other serious (non-fatal/non-life threatening) events must be reported within 4 calendar days of the study chair's observation or awareness of the event to the DSMC chairperson or designee.
 - The study team should report all SAEs and special situations for patients receiving acalabrutinib to Acerta-Pharma per contractual guidelines.
 - The SAE report must include at minimum:
 - **Event term(s)**
 - **Seriousness criteria**
 - **Intensity of the event(s):** Investigator's determination. Intensity for each SAE, including any lab abnormalities, will be determined using the NCI CTCAE version 5.0 as a guideline, whenever possible.
 - **Causality of the event(s):** Investigator's determination of the relationship of the event(s) to study drug administration.
 - **Deaths**
All deaths that occur during the protocol-specified AE reporting period, regardless of attribution,

will be reported to the appropriate parties. When recording a death, the event or condition that caused or contributed to the fatal outcome should be reported as the single medical concept. If the cause of death is unknown and cannot be ascertained at the time of reporting, report "Unexplained Death." Deaths that occur during the protocol specified adverse event reporting period that are attributed by the investigator solely to progression of disease should be recorded only in the study CRF.

- **Hospitalizations for Medical or Surgical Procedures**

Any AE that results in hospitalization or prolonged hospitalization should be documented and reported as an SAE. If a patient is hospitalized to undergo a medical or surgical procedure as a result of an AE, the event responsible for the procedure, not the procedure itself, should be reported as the SAE. For example, if a patient is hospitalized to undergo coronary bypass surgery, record the heart condition that necessitated the bypass as the SAE.

- Hospitalizations for the following reasons do not require reporting:
 - Hospitalization or prolonged hospitalization for diagnostic or elective surgical procedures for pre-existing conditions that have not worsened
 - Hospitalization or prolonged hospitalization required to allow efficacy measurement for the study
 - Hospitalization or prolonged hospitalization for scheduled therapy of the target disease of the study

- **Procedures for Reporting Drug Exposure During Pregnancy**

Female patients of childbearing potential will be instructed to immediately inform the investigator if they become pregnant during the study or until 2 days after the last dose of acalabrutinib or 12 months after the last dose of rituximab. Pregnancy should be confirmed with a serum pregnancy test. The patient should permanently discontinue protocol-indicated treatment. If a woman suspects that she is pregnant while participating in this study, she must inform the investigator immediately and study treatment should be withheld until pregnancy is confirmed by a serum pregnancy test. If serum pregnancy test is positive, the patient should permanently discontinue protocol-indicated treatment.

The investigator or medical designee should counsel the patient, discussing the risks of the pregnancy and the possible effects on the fetus. Monitoring of the patient should continue until conclusion of the pregnancy. All pregnancies of patients taking acalabrutinib or partners of patients taking acalabrutinib as well as related outcomes should be reported to Acerta-Pharma per contractual guidelines. Any SAEs associated with the pregnancy (e.g. an event in the fetus, an event in the mother during or after the pregnancy, or a congenital anomaly/birth defect in the child) should be reported using the SAE form. The pregnancy must be followed for the final pregnancy outcome (i.e., delivery, still birth, miscarriage).

- **Data Safety Monitoring Committee and Institutional Review Board**

Study Investigators will conduct continuous review of data and patient safety. The Investigator will submit quarterly progress reports of these data to the Data Safety Monitoring Committee for review. The review will include for each treatment arm/dose level: the number of patients enrolled, withdrawals, significant toxicities, serious adverse events both expected and unexpected, dose adjustments, and responses observed. The PI maintains a database of all adverse events with toxicity grade and information regarding treatment required, complications, or sequelae. The Investigator will submit a copy of the AE spreadsheet along with a Progress Report to the Data Safety Monitoring Committee (DSMC) for review. Actual review dates will be assigned when the 1st patient is accrued.

- Any serious adverse event that is serious, related AND unexpected must be reported within 5 calendar days to both the DSMC Safety Coordinator and the RSRB (see RSRB guidelines). The DSMC Chair will determine whether further action is required, and when patient safety is of concern, an interim meeting may be called.
- Serious adverse events that are related AND expected or unrelated AND unexpected will be reported to the DSMC for review at the quarterly meeting. SAE reports are expected to include sufficient detail so that the DSMC can determine the severity, toxicity grade, expectedness, treatment required, and a follow up report documenting resolution or if there are sequelae. Serious adverse events that require detailed reports (but not necessarily expedited) are expected, related, non-hematologic toxicities of grades 3, 4 or 5.

The Data Safety Monitoring Committee provides oversight of study progress and safety by review of accrual and events at regularly scheduled meetings. The frequency of review is determined by the size, risk and complexity of the trial, and is assigned by the Protocol Review Committee at the time of their initial review and approval. The Data and Safety Monitoring Committee will monitor all adverse event rates utilizing a cumulative spreadsheet listing of all events submitted along with progress reports by the PI. All serious adverse events that have occurred in the prior 3 months will be reviewed at the regular quarterly meeting of the DSMC in order to confirm toxicity grade, expectedness, relatedness, sequelae, follow up required, and risk to current or future subjects.

- **Food and Drug Administration (FDA)**

In this trial, unexpected adverse events believed to be related to investigational therapy will be reported to the FDA via MedWatch (using the online form currently available at <https://www.accessdata.fda.gov/scripts/medwatch/>), by telephone [name], or by fax [name] (using the form currently available at <http://www.fda.gov/medwatch/report/hcp.htm>).

- **Additional Reporting Requirements for IND**

Events meeting the following criteria need to be submitted to the FDA as expedited IND Safety Reports according to the following guidance and timelines: The Study chair is required to notify the FDA of any fatal or life-threatening AE that is unexpected and assessed to be possibly, probably or definitely related to the investigational agents. An unexpected AE is one that is not listed in the investigator brochure or is not listed at the specificity or severity that has been observed; or, if an investigator brochure is not required or available, is not consistent with the risk information described in the general investigational plan or elsewhere in the current application, as amended. Such reports are to be telephoned or faxed to the FDA within 7 calendar days of first learning of the event.

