Safety data is available combining acalabrutinib with anti-CD20 therapy as well. A phase 1b study of acalabrutinib with obinutuzumab in patients with relapsed as well as previously untreated CLL has enrolled 45 patients to date. (acalabrutinib investigator brochure 7.1) The most frequently reported adverse events were upper respiratory tract infection (68.9%), weight increased (64.4%), diarrhea (62.2%), rash maculopapular (62.2%), cough (55.6%), nausea (51.1%), headache (44.4%), infusion related reaction (44.4%), contusion (42.2%), dizziness (40.0%), vomiting (40.0%), arthralgia, constipation, hypertension, and skin lesion (37.8% each), fatigue (35.6%), decreased appetite, edema peripheral, and sinusitis (33.3% each), fall and oral pain (31.1% each), myalgia (28.9%), and dyspepsia and paresthesia (26.7% each). The most frequently reported Grade ≥ 3 AEs were neutrophil count decreased in 11 (24.4%) subjects, platelet count decreased and syncope in 4 (8.9%) subjects each, and weight increased in 3 (6.7%) subjects. There were no Grade 5 (fatal) AEs reported.

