7.2 STUDY DRUG MODIFICATIONS

- The actions should be taken for any Grade 4 toxicity or unmanageable Grade 3 toxicity. In addition, the actions in Table 7.2.1 should be taken when modification of acalabrutinib dose is recommended for specific treatment-related adverse events as listed in Table 7.2.2.
- If the dose of acalabrutinib is reduced, at the Investigator's discretion, the dose of acalabrutinib may be re-escalated after 2 cycles of a dose reduction in the absence of a recurrence of the toxicity that led to the reduction. Dose changes must be recorded in the study documentation.
- Dose modifications are for adverse events attributed to study treatment. Dose modifications are not required for adverse events unrelated to study treatment.
- Guidance for dose modifications in the event of drug interactions is provided in Table 6.2.1

TABLE 7.2.1: DOSE MODIFICATION ACTIONS FOR ACALABRUTINIB

Event Occurrence	Action
1 st -2 nd	May restart at original dose level (100 mg BID)
3 rd	Restart at 100 mg daily
4 th	Discontinue acalabrutinib

TABLE 7.2.2: STUDY DRUG MODIFICATIONS

	Rituximab	Acalabrutinib
NCI-CTCAE Grade		
Neutropenia		
Grade 3 neutropenia	Maintain current dose	Maintain current dose

	Rituximab	Acalabrutinib
Grade 4 neutropenia lasting >7 days or occurrence of neutropenic fever or infection	Delay rituximab until Grade ≤ 3 and/or neutropenic fever or infection is resolved; thereafter, resume at full dose. If delay is > 4 weeks, discontinue rituximab.	Hold acalabrutinib until recovery of Grade ≤ 3 or baseline. Follow dose modification actions in TABLE 7.2.1.
Thrombocytopenia		
Grade 3 thrombocytopenia	Maintain current dose	Maintain current dose
Grade 4 thrombocytopenia	Delay rituximab until Grade ≤ 3; thereafter resume at full dose. If delay is > 4 weeks, discontinue rituximab.	Hold acalabrutinib until recovery of Grade ≤ 3 or baseline. Follow dose modification actions in TABLE 7.2.1.
Diarrhea (non-infectious)		
Grade 1: increase of <4 stools per day over baseline	n/a	Provide antidiarrheal (eg, loperamide) and maintain current acalabrutinib dose level and schedule.
Grade 2: increase of 4-6 stools per day over baseline	n/a	Provide antidiarrheal (eg, loperamide). Withhold acalabrutinib until Grade ≤ 1. Resume acalabrutinib at current dose level. If rechallenge results in recurrence, may resume at initial or lower dose level at investigator discretion (if applicable). Consider addition of anti-inflammatory (eg, sulfasalazine, budesonide).

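### The plan leaves it to judgment whether an asymptomatic Grade 3 cytopenia is recorded as an adverse event, and no laboratory-based table fills the gap

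*Combined protocol and SAP*

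**What the plan says.** Section 10.5 opens with a broad rule: "All SAEs regardless of grade, severe AEs (i.e. Grade ≥ 3), and events of death will be recorded, regardless of event attribution". Further down, one bullet sets out what need not be noted: "Asymptomatic abnormal laboratory values of Grade 1 or Grade 2 that do not trigger dose interruption or modification of protocol-indicated treatment". These are deemed not clinically significant. The bullet after it carries no grade at all: "Laboratory and vital sign abnormalities are to be recorded as AEs only if they are medically relevant as judged by the investigator". Its examples are symptoms, corrective treatment, discontinuation and a seriousness criterion.

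Section 10.1 defines when a laboratory value is an AE, also without reference to grade. It must cause signs or symptoms, need treatment or further tests, lead to discontinuation or delay, or be a clinically significant change from baseline in the investigator's view.

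Table 7.2.2 keeps both drugs at the current dose for Grade 3 neutropenia and Grade 3 thrombocytopenia. Its only Grade 4 neutropenia row is for "Grade 4 neutropenia lasting >7 days or occurrence of neutropenic fever or infection". Grade 4 thrombocytopenia leads to a delay or hold without a duration condition.

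Section 9.6 bases safety on AEs and on clinically significant laboratory changes. The DSMC "will monitor all adverse event rates utilizing a cumulative spreadsheet listing of all events", which the principal investigator submits with progress reports.

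**The concern.** An exemption limited to Grade 1 and 2 suggests that Grade 3 and higher values are meant to be recorded. The neighboring bullet, and 10.1, let the investigator leave them out. Two people entering the same asymptomatic Grade 3 neutrophil count could follow adjacent bullets and act differently.

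Safety is a secondary objective (2.2), and the hypothesis in 1.6 looks to shorter and less toxic therapy. The background in 1.4 suggests that the events affected are not rare. In the cited study of acalabrutinib with another anti-CD20 antibody, the leading Grade 3 or higher event was "neutrophil count decreased in 11 (24.4%) subjects". In the pooled monotherapy data it was neutropenia, at 10.4%. If the recording of such values depends on judgment in an open-label trial, the AE-based cytopenia rate may be too low, and the DSMC's AE listing would share the deficit.

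**Working it through.** **Step 1. The recording rules applied to each type of finding.** Take a value with no symptoms and no treatment given. Inputs are 10.1, 10.5, the first bullet of 7.2 and Table 7.2.2. The table is headed with NCI-CTCAE grades, whereas 10.1 sends hematologic toxicity to Appendix 2. Reading one across to the other grade for grade is an assumption.

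| Finding | Dose action in Table 7.2.2 | Recorded as an AE? |
|---|---|---|
| Grade 1–2, no dose action | – | No, exempt by rule |
| Grade 3 neutropenia | None, either drug | By judgment |
| Grade 3 thrombocytopenia | None, either drug | By judgment |
| Grade 3 anemia | No row (catch-all is non-hematologic) | By judgment |
| Grade 4 neutropenia, 7 days or less, no fever or infection | No row | Unclear: the first bullet of 7.2 calls for action at any Grade 4 toxicity, the table does not |
| Grade 4 neutropenia, longer than 7 days, or with fever or infection | Delay/hold | Yes, delay limb of 10.1 |
| Grade 4 thrombocytopenia | Delay/hold | Yes, delay limb of 10.1 |

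The gap is therefore asymptomatic Grade 3 cytopenias, plus short uncomplicated Grade 4 neutropenia if the table governs.

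**Step 2. Whether a planned output closes the gap.** Section 9.6 tabulates AEs and laboratory changes judged clinically significant, and specifies no grade-based laboratory table. Table 5.1 schedules hematology at screening, through cycle 1, on day 1 of cycles 2 to 12, and every 3 months to cycle 24. The raw values therefore exist, but no planned summary uses them irrespective of judgment.

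**Step 3. Size.** The plan gives no figure for this point. The background figure reproduces: 11/45 = 24.4%. Let *p* be the true proportion of patients with Grade 3 or higher neutropenia and *u* the share of those patients whose events are never entered. The expected number recorded among 40 is 40 × *p* × (1 − *u*). The documents give no value for *u*, so it runs from 0 to 1. Counts are rounded, with exact (Clopper-Pearson) 95% intervals.

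- *p* = 24.4%, *u* = 0: 40 × 0.244 = 9.76, so 10/40 = 25.0% (12.7% to 41.2%).
- *p* = 24.4%, *u* = 0.5: 4.88, so 5/40 = 12.5% (4.2% to 26.8%).
- *p* = 24.4%, *u* = 0.75: 2.44, so 2/40 = 5.0% (0.6% to 16.9%).
- *p* = 10.4%, *u* = 0: 40 × 0.104 = 4.16, so 4/40 = 10.0% (2.8% to 23.7%).
- *p* = 10.4%, *u* = 0.5: 2.08, so 2/40 = 5.0% (0.6% to 16.9%).
- Either *p*, *u* = 1: 0/40 (upper limit 8.8%).

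These lines show how the rate responds to *u*. They do not predict it.

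**The case against.** The sponsor can fairly say that the rules fit together. The opening sentence of 10.5 concerns severe AEs, and a value must first be an AE under 10.1. On that reading, Grade 1–2 values are out by rule and higher grades are judged. This stands as logic, so a reader who infers an outright contradiction goes too far. It does not settle what the Grade 1–2 limit is meant to imply, and it confirms that Grade 3 values enter by judgment.

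A reader might also infer that Grade 3 and 4 cytopenias as a class usually trigger no dose action and so usually vanish. The documents do not support that. Grade 4 thrombocytopenia and prolonged or complicated Grade 4 neutropenia lead to a hold and qualify under 10.1. The further-tests limb of 10.1 and the supportive care to be considered from Grade 2 (7.1) bring in other cases. The examples in 10.5 are not exhaustive.

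The rates of 24.4% and 10.4% are themselves reported AE rates, and the recording rules behind them are not given. The first also comes from a different antibody and a mixed relapsed and untreated population. They cannot be treated as true rates that this trial would then halve.

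Finally, the DSMC is not blind: its quarterly review also covers significant toxicities and dose adjustments. Safety is descriptive in a single-arm trial, no numerical stopping threshold uses this rate, and the primary endpoint is untouched. All of this stands and limits the weight of the point.

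**Conclusion.** The point holds in a limited form. For asymptomatic Grade 3 cytopenias, and for short uncomplicated Grade 4 neutropenia if Table 7.2.2 governs, AE recording is unclear and discretionary. The AE-based rates in 9.6 and the DSMC's AE spreadsheet can therefore understate Grade 3 or higher cytopenia. The direction is clear, since omission can only lower the rate. The amount is not known: between none and all of these events. The illustration depends wholly on assumed values of *p* and *u*.

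A reader might conclude that the data are lost. They are not: the counts are collected through cycle 24 while a patient is on treatment, and only the judgment-based summaries can miss them. That makes this a worthwhile improvement to the safety analysis at low cost, with no bearing on the complete response analysis.

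**What to change.** 1. **Section 9.6.** Add a table of worst post-baseline grade per patient for ANC, platelets and hemoglobin, shown against baseline. Derive it from all collected hematology results, scheduled or not, whether or not an AE was entered. Grade by Appendix 2 and apply its not-evaluable exceptions. For example, patients with pretreatment ANC below 1 × 10⁹/L are not evaluable for ANC toxicity, and eligibility admits ANC from 0.5 × 10⁹/L. State the evaluable denominator for each parameter. Without these exceptions, baseline disease cytopenia would inflate the rate.
2. **DSMC.** Send the same table with each quarterly report.
3. **Sections 10.1 and 10.5.** Align the wording so that both give one answer for Grade 3 or higher laboratory values. Changing 10.5 alone would leave the restrictive definition in 10.1 in force and create a real conflict.
4. **Section 7.2.** Separately, the bullet on any Grade 4 toxicity and the more-than-7-days condition in Table 7.2.2 must be reconciled. This review takes no view on which should prevail.

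The cost is one derived table from data already collected and some wording. The reported Grade 3–4 cytopenia rate may be higher. The table ends where laboratory collection ends (cycle 24 or discontinuation of therapy) and cannot show low counts that fall between blood draws.
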